5.1. DEFINITIONS	Error! Bookmark not defined.
5.2. REPORTING PROCEDURES	Error! Bookmark not defined.
6. ASSESSMENT AND FOLLOW-UP	9
7. STATISTICS AND DATA ANALYSIS	9
8. REGULATORY ISSUES	10
8.1. ETHICS APPROVAL	10
8.2. CONSENT	10
8.3. CONFIDENTIALITY	10
8.4. INDEMNITY	10
8.5. SPONSOR	11
8.6. FUNDING	11
8.7. AUDITS	11
9. STUDY MANAGEMENT	11
10. PUBLICATION POLICY	11

TITLE	Qualitative study to determine how Chronic Kidney Disease is managed by healthcare professions in primary care.
DESIGN	Qualitative
AIMS	To better understand how healthcare providers in primary care within the National Health System in the United Kingdom, manage Chronic Kidney Disease (CKD). Through this we hope to be able to identify ways in which we can improve the overall care of patients with CKD.
OUTCOME MEASURES	The primary outcome measure is to determine current understanding on the management of CKD and to identify ways in which the screening, diagnosis, and management of patients at risk of CKD can be improved upon.
POPULATION	Doctors, clinical pharmacists, and advanced nurse practitioners, working in primary care.
ELIGIBILITY	Primary care doctors (General practitioners) and health care providers (clinical pharmacists, and advanced nurse practitioners working in primary care across the United Kingdom.
DURATION	6 months

1. INTRODUCTION

1.1. BACKGROUND

15% of the population in England aged >35 years of age have Chronic Kidney Disease (CKD). This results in 45,000 premature deaths, 100,000 excessive hospitalisations and £1.45 billion in costs to the NHS per year. Type 2 Diabetes is the commonest cause, with other common causes for CKD including but not limited to hypertension, ischaemic heart disease, heart failure and multisystemic disorders.

With the rising prevalence of diabetes, hypertension, and ischaemic heart disease amongst other clinical risk factors for CKD, the prevalence of CKD is expected to increase, with a substantial proportion of patients developing cardiovascular complications or progressing to ESRD. Primary care is instrumental in the screening of patients for CKD in the presence of known clinical risk factors as well as the early and effective management of confirmed CKD with prognostically beneficial medication. With prior working by myself highlighting the lack of screening of patients for CKD in the presence of clinical risk factors for CKD in North West London, alongside poor prescribing practices of prognostically beneficial medications. We therefore aim to better understand how healthcare professionals working in primary care could be better supported to screen patients for CKD and ensure appropriate subsequent management.

1.2. RATIONALE FOR CURRENT STUDY

Chronic Kidney Disease is a progressive condition that affects more than 10% of the general population worldwide, resulting in in excess of 800 million people currently affected. With the rising prevalence of Type 2 Diabetes, hypertension and ischaemic heart disease amongst other clinical risk factors for CKD, the prevalence of CKD over the coming ten years is expected to increase 2-3 fold. CKD is associated with significant degree of morbidity with patients not only going on to develop end stage renal disease, but also an array of cardiovascular diseases, resulting in premature morbidity and mortality resulting in an overall poor quality of life.

Primary care is vital in the 1. screening of patients with clinical risk factors for CKD 2. Diagnosis and coding of CKD and 3. Management of CKD. However, through prior work done by our group, we have identified poor screening of patients with clinical risk factors for CKD, poor coding of patients post diagnostic tests confirming CKD, poor communication with patients with regards to CKD diagnosis, cause and long term outcome in addition to inadequate prescribing of prognostically beneficial medication. This study therefore aims to determine how healthcare professionals in primary care screen for, diagnose and manage CKD in the community. Furthermore, it aims to determine areas done well as well as areas where improvement is needed to improve a patient's clinical journey and management. This will be done in the form of an online questionnaire and focus groups, advertised via Integrated Care Boards (ICB's) across the United Kingdom. Through this, we hope to gain further insight into areas of clinical management done well and areas of improvement as well as how primary care feel current management could be improved upon, obstacles faced, additional resources required and how they could be better supported by hospital specialists. Study results will be analysed and published in a peer reviewed journal with recommendations made with regards

to how care should be altered to help delay and prevent CKD onset and progression alongside the associated health care complications.

2. STUDY OBJECTIVES

The main research objective is to determine the current understanding amongst primary care health care professionals with regards to the screening and management of CKD, in addition to developing an understanding of the barriers faced by primary care in ensuring optimal clinical care. By gaining a better understanding of how GPs looking after patients with risk factors for CKD/confirmed CKD manage their patients, we hope to be able to identify areas of improvement, in order to create change and prevent the onset and progression of CKD.

3. STUDY DESIGN

The study is designed in the form of an online questionnaire, with participants recruited through advertisement of the study through ICB's across the United Kingdom. Qualiatics.com will be utilised to create and share the questionnaire, with participants expected to take to 15 minutes to complete the questionnaire in total. The main research objective is to identify ways in which the management of patients with clinical risk factors for CKD can be improved upon in primary care. By gaining a better understanding of the barriers faced by healthcare professionals in primary care will allow us to identify new ways in which to improve patient care and management. Furthermore, we will seek to better understand ways in which healthcare professionals in primary care feel they could be better supported to prevent or delay progression of CKD and associated complications. Their views on the use of a risk prediction score and biomarkers for the diagnosis and assessment of progression will be sought as well as their opinions on the use of digital health within primary care for patients with CKD.

The study will be validated by primary and secondary care clinicians. Following validation and HRA approval, Integrated care boards (ICBs) across the UK will be sent an online link to the questionnaire and requested to share amongst health care providers within their ICB. The participant information sheet will be presented electronically, and participants consented electronically utilising Qualiatics.com. Participants will be asked if they are willing to partake in an online focus group (lasting up to 1 hour in total) to further discuss the study and gain a further understanding of how care could be improved. For those willing to take part, an email address contact will be requested as a mode of communication between study organisers and participants. Participation is completely voluntary, and participants may change their decision at any time. Participants can withdraw consent at any time prior to the end of the focus group and can leave the session without any explanation. There is no financial incentive for clinicians partaking in the focus groups. Focus groups will be recorded utilising Microsoft Teams, with focus groups transcribed anonymously within 1 week of the focus group and the recording subsequently deleted. The

transcribed focus group will be deleted from records within 1 week, with the transcription stored electronically on the Imperial College Server.

Data from both components of the study will subsequently be analysed, with recommendations made of changes required to improve the screening and management of patients at risk of CKD.

4. PARTICIPANT ENTRY

4.1. PRE-REGISTRATION EVALUATIONS

No tests are required to be done prior to the patient entering the study.

4.2. INCLUSION CRITERIA

Doctors, clinical pharmacists, and advanced nurse practitioners, working in primary care.

4.3. EXCLUSION CRITERIA

Secondary care health care professionals.

4.4. WITHDRAWAL CRITERIA

Participants can withdraw at any point prior to submission of the online questionnaire. Questionnaires left prior to completion, will not be submitted and no data will therefore be retained. Once submitted, responses cannot be withdrawn as all data is collated collectively and anonymously. With regards to the focus group, participants can exist the online focus group at any time without explanation. Where participants withdraw, responses given by the individual will no longer be transcribed and considered. Once the focus group is transcribed and focus group recording deleted, it will not be possible to withdraw responses due to the anonymous nature in which the focus group will be transcribed prior to its deletion.

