6. ASSESSMENT AND FOLLOW-UP

Given the nature of the study, an online anonymous questionnaire/focus group there will be no follow up or assessment of study participants.

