7. STATISTICS AND DATA ANALYSIS

This is a qualitative study, with qualitative methods applied to analyse the data generated. The qualitative data analysis approach will systematise descriptive data collected through the online questionnaire and subsequent focus groups, with the aim being to identify patterns and themes behind the interviews, surveys, and observations and interpreting it. The method aims to identify patterns and themes behind textual data. Specific analysis undertaken will utilise: 1. Discourse analysis whereby we will review the received answers from the questionnaire and the transcript from the focus groups to determine relationships between the received information and its context. 2. Conversion of qualitative data within the online questionnaire to quantitative data to allow for conclusions to be made 3. Thematic analysis for the transcript of the focus group to identify themes on how patients feel their care would have been improved upon.

Data and all appropriate documentation will be stored for a minimum of 10 years after the completion of the study, including the follow-up period.

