8.2. CONSENT

Consent to enter the study must be sought from each participant only after a full explanation has been given, an information leaflet offered and time allowed for consideration. Participant consent will be obtained electronically utilising Qualiatics.com. The right of the participant to refuse to participate without giving reasons must be respected. All participants are free to withdraw at any time from the protocol without giving reasons and without prejudicing further treatment.

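### Does discarding unfinished questionnaires leave the quantified survey results without a completion rate?

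*Protocol*

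**What the plan says.** Section 4.4 lets a questionnaire participant leave until the form is sent: "Participants can withdraw at any point prior to submission of the online questionnaire". It then states the consequence of leaving early: "Questionnaires left prior to completion, will not be submitted and no data will therefore be retained". Once sent, answers cannot be taken out, because they are pooled anonymously. Section 8.2 gives the general right: "All participants are free to withdraw at any time from the protocol without giving reasons".

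Section 3 describes how the survey reaches people. Integrated Care Boards (ICBs) "will be sent an online link to the questionnaire and requested to share amongst health care providers within their ICB". No number of people invited is given. Consent happens inside the questionnaire tool, as Section 3 says ("participants consented electronically utilising Qualiatics.com") and Section 8.2 repeats ("Participant consent will be obtained electronically utilising Qualiatics.com").

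Section 7 calls the study qualitative and lists three analyses. One of them is: "Conversion of qualitative data within the online questionnaire to quantitative data to allow for conclusions to be made". Section 6 adds that "there will be no follow up or assessment of study participants". No section mentions a response rate, a completion rate or a count of starts.

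**The concern.** Three features of the protocol combine. Nothing is kept from people who stop part-way. The survey answers are to be quantified, and published recommendations are to follow. The link is passed on by third parties, so the number invited is not recorded in the plan. Anyone reading the resulting percentages would want to know how many people began and did not finish, since those who stop may differ from those who submit.

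Timing matters as well. An analysis plan written later can say how to report a completion rate, but it cannot recover a count that was never kept. With no follow-up, people who leave cannot be described afterwards either. If Section 4.4 forced deletion of every trace of an unfinished form, the quantified results could not be bounded for non-completion.

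**Working it through.** **The plan's own figures.** The protocol gives no sample size, expected response, completion rate or target proportion. There is nothing to reproduce, so what follows is an illustration on assumed inputs plus a reading of the text.

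**Inputs (all assumed).** Let p be the share of submitters reporting a practice (70% or 50%), and let a be the share of starters who leave (10% to 40%).

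**Formula.** Submitters make up (1 − a) of starters and contribute p(1 − a). If none of those who left follow the practice, the share among all starters is p(1 − a). If all of them do, it is p(1 − a) + a. The width is therefore a, whatever p is.

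| p | a | lower = p(1 − a) | upper = lower + a |
|---|---|---|---|
| 70% | 10% | 0.70 × 0.90 = 63% | 73% |
| 70% | 20% | 0.70 × 0.80 = 56% | 76% |
| 70% | 30% | 0.70 × 0.70 = 49% | 79% |
| 70% | 40% | 0.70 × 0.60 = 42% | 82% |
| 50% | 10% | 0.50 × 0.90 = 45% | 55% |
| 50% | 40% | 0.50 × 0.60 = 30% | 70% |

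The arithmetic is sound, and without a count of starts a reader could not say which row applies. Whether this calls for a change depends on four further points.

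**1. Does Section 4.4 remove the count?** The clause on retaining nothing is drawn as a consequence of the form not being submitted. What goes unsubmitted is a set of answers. A tally of how many people consented or opened the form contains no answers, and the sentence does not address it. Section 3 and Section 8.2 place consent on the same platform, so consents can be set against submissions. Section 7 requires study data and documentation to be stored for at least 10 years. It does not say whether consent records of people who leave are included. The text is silent on the count and does not prohibit it.

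**2. Is the number of starts the only possible denominator?** No. Section 3 has the ICBs circulate the link, and nothing stops the study team from asking them how many people they sent it to. The protocol does not record such a number, but that does not make it unobtainable.

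**3. What would the count change?** Under the plan as written, the coded answers, themes and conclusions come from submitted questionnaires and focus-group transcripts. With a count of starts they come from exactly the same material. The count adds one descriptive percentage. The protocol states no prevalence estimate, interval or test that would be recomputed from it.

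**4. Do the bounds concern the right population?** They describe everyone who opened the questionnaire. Section 4.2 defines the population as doctors, clinical pharmacists and advanced nurse practitioners in primary care. Who chooses to open a shared link is a separate matter, and a completion rate says nothing about it. The count itself would be imprecise too: with anonymous access through a shared link, someone who stops and comes back may be counted twice, which would overstate a and widen the ranges above.

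**The case for a change.** The best argument for changing the protocol is that the retention rule sits there and takes effect when the platform is set up. Someone configuring the tool could fairly read Section 4.4 as requiring every unfinished record to be deleted, including the record that it was opened. That loss would be permanent. Calling the study qualitative is not a full answer, because Section 7 does plan to quantify the survey and the results are to support recommendations on care. A clarifying phrase would cost very little.

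Part of this stands. The protocol does not say whether starts are counted, a lost count could not be rebuilt, and a survey report is better with a completion rate than without one. It does not show an error, however. The strict reading is possible but not the natural one, and no other section contradicts the sentence. Discarding the answers of people who leave is itself a reasonable withdrawal rule, given that submitted answers cannot be withdrawn later. Reporting completion is also the kind of detail commonly settled in an analysis plan or the survey set-up, and the analysis plan is not at hand.

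Adding a statement that starts are recorded, while leaving the existing clause unchanged, would bring its own difficulty. Section 4.4 would then appear both to keep nothing and to keep something. Keeping professional role or the last page reached would go further than a bare count and would sit less easily with the withdrawal rule.

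**Conclusion.** No change to the plan is needed. The protocol is silent on a count of starts but does not exclude one, and a study team can take it from the electronic consent step without altering the withdrawal rule. The consequence of the silence is small. The material analysed and the conclusions drawn are the same either way, and what is at stake is one descriptive figure in the report.

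The illustrated ranges, 10 percentage points wide if 10% leave and 40 points wide if 40% leave, rest entirely on assumed values. They assume no direction of bias and apply to starters only. The conclusion rests on reading the no-data clause as referring to unsubmitted answers, and on the protocol's quantified survey results being descriptive, with no stated estimate, test or sample size. If the study later presented survey percentages as prevalence estimates, a completion rate would matter more, although self-selection through the shared link would remain a limitation it could not address.

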5. ADVERSE EVENTS

Not applicable.

6. ASSESSMENT AND FOLLOW-UP

Given the nature of the study, an online anonymous questionnaire/focus group there will be no follow up or assessment of study participants.

7. STATISTICS AND DATA ANALYSIS

This is a qualitative study, with qualitative methods applied to analyse the data generated. The qualitative data analysis approach will systematise descriptive data collected through the online questionnaire and subsequent focus groups, with the aim being to identify patterns and themes behind the interviews, surveys, and observations and interpreting it. The method aims to identify patterns and themes behind textual data. Specific analysis undertaken will utilise: 1. Discourse analysis whereby we will review the received answers from the questionnaire and the transcript from the focus groups to determine relationships between the received information and its context. 2. Conversion of qualitative data within the online questionnaire to quantitative data to allow for conclusions to be made 3. Thematic analysis for the transcript of the focus group to identify themes on how patients feel their care would have been improved upon.

Data and all appropriate documentation will be stored for a minimum of 10 years after the completion of the study, including the follow-up period.

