10. PUBLICATION POLICY

Study results will be analysed and published in a peer reviewed journal with recommendations made with regards to how care should be altered to improve the screening, coding and management of individuals with clinical risk factors for CKD/confirmed CKD.

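### Do the questionnaire counts need a record of which ICBs forwarded the link and how many clinicians it reached?

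*Protocol*

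**What the plan says.** Section 7 of the protocol opens with the statement "This is a qualitative study, with qualitative methods applied to analyse the data generated". It then names three analyses: discourse analysis of questionnaire answers and focus-group transcripts, a quantitative step, and thematic analysis of the focus groups. The quantitative step, item 2, reads "Conversion of qualitative data within the online questionnaire to quantitative data to allow for conclusions to be made".

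Under Section 3, ICBs across the UK "will be sent an online link to the questionnaire and requested to share amongst health care providers within their ICB". On what is kept, Section 4.4 states "Questionnaires left prior to completion, will not be submitted and no data will therefore be retained" and "Once submitted, responses cannot be withdrawn as all data is collated collectively and anonymously". Section 8.3, by contrast, describes the data as pseudonymised.

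On use of the results, Section 3 says "Data from both components of the study will subsequently be analysed, with recommendations made of changes required", and Section 10 promises "recommendations made with regards to how care should be altered to improve the screening, coding and management of individuals". The aim in the synopsis is "To better understand how healthcare providers in primary care within the National Health System in the United Kingdom, manage Chronic Kidney Disease".

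No section mentions a forwarding confirmation, a number of clinicians approached, a target sample or a response rate.

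**The concern.** Item 2 is the one place where the protocol turns answers into numbers and says that conclusions will be drawn from them. The respondents are volunteers who answered a link passed on at each ICB's discretion. If nobody records which ICBs passed it on, or to roughly how many eligible clinicians, a reader who sees that a certain share of respondents gave an answer cannot judge how selected those respondents are.

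The aim is worded for UK primary care as a whole, and the results feed published recommendations. There is thus a risk that counts from a self-selected group are read as a picture of the profession. The gap also lies in recruitment and data capture, so an analysis plan written later could not create the information by itself.

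**Working it through.** The protocol gives no sample size, response rate or other figure that could be reproduced. The check is therefore a comparison of passages, with two small illustrations.

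**1. What the team would hold.** Five figures connect the invitation to a reported count. The list is a reviewer's construction; the protocol does not set it.

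| Figure | Held as written? | Basis |
|---|---|---|
| ICBs sent the link | Yes | Section 3: the study sends it |
| ICBs that forwarded it | Not planned | Section 3: sharing is requested only |
| Eligible clinicians reached | Not planned | Section 3 |
| Questionnaires started | No | Section 4.4: unfinished ones leave no data |
| Questionnaires submitted | Yes | Section 4.4 |

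This gives 2 of 5 held. A log of ICB returns would add the second and third, approximately: 2 + 2 = 4 of 5. Some coverage information therefore exists already, namely the number of ICBs invited. What is absent is the forwarding confirmation and the clinician denominator.

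**2. What a denominator would tell a reader (assumed values, not from the documents).** Let p be the share of respondents giving an answer and f the fraction of clinicians reached who respond. With nothing assumed about non-respondents, the share among all clinicians reached lies between f·p and f·p + (1 − f). Take p = 0.60:

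- f = 0.05: 0.05 × 0.60 = 0.03, and 0.03 + 0.95 = 0.98, so 3% to 98%
- f = 0.20: 0.20 × 0.60 = 0.12, and 0.12 + 0.80 = 0.92, so 12% to 92%
- f = 0.50: 0.50 × 0.60 = 0.30, and 0.30 + 0.50 = 0.80, so 30% to 80%

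Even at a 50% response the interval is 50 percentage points wide. Knowing f would show how weak an extrapolation is; it would not make one sound. The quantity bounded here, the share among all clinicians reached, is also one that the protocol never undertakes to estimate.

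**3. Whether a log would give a dependable rate.** ICB returns would be voluntary and rough. If some ICBs make no return, the reach is understated and the calculated rate is too high. If the ICBs that do reply overstate their reach, through overlapping lists or ineligible recipients, the error goes the other way. For illustration, suppose 1,000 are reported reached, 500 of them truly were, and 200 more were reached through ICBs that made no return. The calculated rate is replies/1,000, while the true rate is replies/(500 + 200) = replies/700, which is larger. The rate could not even be labelled safely as an upper limit.

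**4. Whether the replies could help.** Anonymity does not stop a questionnaire from asking for ICB, region or role. The questionnaire is not shown. If it asks, the replies themselves would show many of the ICBs that forwarded the link. Sections 4.4 and 8.3 also differ on whether data are anonymous or pseudonymised, so it is not established that replies cannot be tied to an ICB.

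**5. What changes in the results.** The discourse and thematic analyses need no response rate. Item 2 yields counts of coded answers among those who replied, and those counts are the same with or without a log. The point bears on 1 of 3 analyses, and there only on how counts are described.

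**The case for a change.** The strongest case for a change is that it would be cheap and is easiest to make before launch: one request in the message that already carries the link, and a sentence each in Sections 3 and 7. The questionnaire is the main instrument, the objectives speak of primary care professionals in general, and the results lead to recommendations on care. Participation is voluntary and unpaid, so self-selection is plausible. An analysis plan can say how counts are reported, but it cannot recover information that was never requested.

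Part of this stands. The protocol does omit forwarding and reach, and asking when the link goes out would be good practice. The information is not lost if the request is left out, however, because the team knows which ICBs it contacted and can ask them later. The return would be approximate, would depend on goodwill in a study without dedicated funding, and might end in a statement that no rate can be calculated, which needs no log. Limiting the counts to respondents is an ordinary reporting caveat that can be made in the analysis or the paper.

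**Conclusion.** The omission is real but does not call for a change to the plan. Followed as written, the study would produce sound descriptive counts and themes of what respondents said, together with the number of ICBs invited and the number of questionnaires submitted. It would lack a clinician denominator, which matters only if the counts are presented as estimates for UK primary care, and the protocol makes no such claim. The effect is confined to the interpretation of one of three analyses. No bias can be sized from the documents, and the ranges above rest on assumed values.

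This conclusion assumes that the report treats item 2 counts as describing respondents and does not generalise them. A team that wishes to may ask ICBs about forwarding and approximate reach when it sends the link, and should then give any response rate as approximate only. That is optional and would alter no result.

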8.6. FUNDING

There is no specific funding for this study. There are no investigator payments. Health care professionals undertaking the questionnaire and focus groups will not receive any payment for their participation.

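### Section 7 aims the thematic analysis of the focus groups at patients' feelings, but only primary care professionals take part

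*Protocol*

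**What the plan says.** Section 7 of the protocol opens with a general aim of finding patterns and themes in the questionnaire and focus-group material, then names three analyses:

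1. A discourse analysis of both sources: "Discourse analysis whereby we will review the received answers from the questionnaire and the transcript from the focus groups".
2. A conversion of the qualitative questionnaire data into quantitative form.
3. A thematic analysis of the focus groups: "Thematic analysis for the transcript of the focus group to identify themes on how patients feel their care would have been improved upon".

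The eligible participants in Section 4.2 are "Doctors, clinical pharmacists, and advanced nurse practitioners, working in primary care", and the population entry in the synopsis says the same. Section 8.6 confirms who takes part in both components: "Health care professionals undertaking the questionnaire and focus groups will not receive any payment for their participation".

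The aims are also framed around professionals. Section 1.2 wants to learn "how primary care feel current management could be improved upon, obstacles faced, additional resources required". Section 2 includes "developing an understanding of the barriers faced by primary care in ensuring optimal clinical care". Section 3 looks for "ways in which healthcare professionals in primary care feel they could be better supported to prevent or delay progression of CKD".

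**The concern.** The third analysis is given a question about people who do not speak in the transcript. A thematic analysis is coded and reported against its stated question, so the subject of that question matters. An analyst who follows the sentence has two options. One is to find that the transcript holds no patient statements, so the step has no result. The other is to code what clinicians say about their patients and report it as how patients feel. The second would misattribute the source in a paper that, under Section 10, is to make recommendations on how care should change.

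This is also the only listed step whose stated product is themes from the focus groups on improving care. The discourse analysis uses the same transcript, but its stated purpose is to relate the information received to its context.

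**Working it through.** The protocol gives no figure on this point, so there is nothing to recompute. The check sets the sections side by side.

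**Who speaks in the transcript**

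| Place in the protocol | What it establishes |
|---|---|
| Synopsis (population, eligibility) and Section 4.2 | Only primary care doctors, clinical pharmacists and advanced nurse practitioners are eligible |
| Section 4.3 | Secondary care professionals are excluded; patients are not mentioned as a group |
| Section 3, recruitment | The link goes to Integrated Care Boards, which pass it to health care providers |
| Section 3, focus groups | Members are questionnaire participants who volunteer, and are called clinicians |
| Section 8.6 | Those taking part in the questionnaire and focus groups are health care professionals |

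No section describes a patient group, patient recruitment or a patient data source. The transcript therefore contains professionals' statements only.

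**Whose views the study seeks**

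| Place in the protocol | Whose view |
|---|---|
| Synopsis, outcome measures | Current understanding of CKD management; the holder is not named, but the population entry is professionals |
| Section 1.2 | Primary care's view of how management could improve, the obstacles and the resources needed |
| Section 2 | Professionals' understanding and the barriers primary care faces |
| Section 3 | Professionals' view of how they could be better supported |
| Section 7, third analysis | Patients' view of their care |

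Section 1.2 and the third analysis ask nearly the same question with different subjects: primary care in one, patients in the other. Only the Section 7 version conflicts with the eligibility criteria, and nothing elsewhere corrects it.

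**How far the error reaches**

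| Listed analysis | Questionnaire | Transcript | Aimed at patients |
|---|---|---|---|
| 1. Discourse | yes | yes | no |
| 2. Conversion | yes | no | no |
| 3. Thematic | no | yes | yes |

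- All listed analyses: 1 of 3 affected.
- Analyses that use the transcript (1 and 3): 1 of 2 affected.
- Analyses that use the questionnaire (1 and 2): 0 of 2 affected.

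These counts show where the error sits. They do not measure how much of the study is compromised, because the method and data source of the third analysis are sound and only its stated target is wrong.

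**The case against.** The strongest reply is that this is a slip of wording. Patient language also appears in Section 4.1, which speaks of a patient entering the study, and in Section 8.2, which refers to further treatment. Neither sets up a patient arm, and both read like text carried over from a template. On this view a reader of the whole protocol would know whose views are meant. The general aim in Section 7 also covers themes without mentioning patients, and neither Section 1.2 nor Section 10 promises a report of patient views. Changing one noun would then be enough.

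Much of this stands. The wording probably is a carry-over, the intent can be recovered, and misattribution in the final report is a risk rather than a certainty. It does not remove the point. The phrases in Sections 4.1 and 8.2 sit in screening and consent text, whereas this one states what an analysis is for. The general aim does not override the specific target given to the third analysis.

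A second reply is that clinicians could report patients' feelings by proxy. The protocol does not say so, and the sentence most naturally means the patients' own view. If proxy reports were intended, that would have to be stated.

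On the length of the fix, a bare substitution would remove the contradiction. The fuller sentence proposed below adds only aims that the protocol already states.

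**Conclusion.** The concern holds. The stated target of the thematic analysis contradicts the eligibility criteria, the recruitment route, the make-up of the focus groups and the study objectives. It should be fixed, but it does not undermine the study. The primary outcome, "The primary outcome measure is to determine current understanding on the management of CKD", can still be addressed: the discourse analysis also covers the transcripts, the general aim is not tied to patients, and the questionnaire analyses are untouched. No numerical result changes.

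The conclusion rests on two readings of the text: that the focus groups contain only the professionals described in Sections 3, 4.2 and 8.6, and that the sentence refers to patients' own views rather than views reported for them. The first is stated directly; the second is the natural sense of the words.

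**What to change.** Replace the third analysis in Section 7 with a sentence such as:

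> Thematic analysis of the focus-group transcripts to identify themes in healthcare professionals' understanding of CKD screening, diagnosis and management, the barriers they face, the support they need, and how they feel care could be improved.

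Each element comes from the synopsis or Sections 1.2, 2 and 3. If patient views really are wanted, the protocol would instead need a patient data source, which it does not have now.

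The cost is one sentence, with no new data and no change to recruitment, data collection or the other two analyses. It should be made before coding starts. Sections 3 and 4.4 have the recordings deleted after anonymous transcription, so the transcript becomes the remaining focus-group source and should be coded against the right question from the outset.
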